#### *4.4 Location*

The AO imagers and Heidelberg Spectralis high resolution OCT system are housed in the FDA/CDRH/OSEL laboratory space on the White Oak Campus, Building 62, Room G238.

#### *4.5 Study Duration*

The duration of the study, including data collection, analysis, and dissemination, is expected to last five years.

### **5.0 Data Management Plan**

#### *5.1 Storage of Data and Samples*

No blood, tissue or other samples will be collected or stored in this study. Patient records from the initial UMEA eye exam will be kept at the eye clinic as described in Section 5.3. Clinical retinal images and data will be transferred on an external hard drive to the FDA investigators with subject consent (Appendix 9). De-identified images (that contain only the subject number but no personal information) will be stored only on an external hard drive (i.e., not transferred to an FDA computer) and stored in a locked file cabinet in the FDA PI's office ([name]). The clinical data and images will be de-identified by [name].

The only site of AO data and image collection will be the optical diagnostics devices laboratory of FDA/CDRH/OSEL/DBP on the White Oak Campus. The acquired data will be initially stored on the AO system computer, which is password protected. Because of the potential size of volumetric image datasets, which can be tens of gigabytes for a single subject for a single imaging session or more, de-identified data will be transferred to a shared network drive, which is password protected and accessible only from FDA scientific computers.

#### *5.2 Privacy*

All research activities will be conducted in a private setting, with only the subject and investigators in the imaging laboratory.

#### *5.3 Confidentiality*

All records will be kept confidential and will only be reviewed by [name]. Printed, signed informed consent forms will be stored in a locked file cabinet in the PIs office ([name]). The Certificate of Confidentiality issued by the FDA in accordance with new requirements under the 21st Century Cures Act is included in Appendix 10.

For the initial UMEA eye exam, records will be kept at the eye clinic in the same manner as records from patients in the clinical practice. Most patient information is recorded in paper files that are kept in locked cabinets. Some information is collected in encrypted electronic records, which are stored on password protected computers. Except de-identified clinical data and retinal images discussed above in Section 5.1, all patient information remains on-site at the UMEA eye clinic and is accessible only by trained staff and maintained with confidentiality abiding by HIPAA and all relevant regulations regarding medical records. Records for the initial eye exam will be kept together with records from the clinical practice and destroyed seven (7) years after initial collection.

FDA staff are considered a vulnerable population because of their close working relationship with the FDA investigators. Therefore, confidentiality of potentially sensitive and private information about co-workers requires heightened vigilance. To mitigate risk of a confidentiality breach, this study is designed to minimize personal identifiable information (PII) and private health information (PHI) data collection and to consolidate PII and PHI data storage in only one electronic location kept by the PI ([name]). Furthermore, all study staff have been instructed not to discuss any study patient information with co-workers or in a regular work environment.

For the FDA imaging session, the only PII collected from the subjects will be name and age. A participant's age and sex will be collected to ensure a diverse population is represented and also potentially to compare retinal images across different age groups. A subject number will be assigned to each participant and all information collected during the imaging session (image videos and ocular aberration data) will be coded using their subject number. The only link between patient number and PII (name and age) will be a single cross-referenced list, which will be kept in a password-protected excel spreadsheet. Any data publicly disclosed cannot be linked back to the subject. Only the study investigators will have access to this electronic document.

#### *5.4 Analysis Plan*

De-identified data, particularly OCT and SLO videos will be analysed with custom software written by the investigators in LabVIEW and MATLAB or commonly available image processing (ImageJ, Photoshop) and statistical programs. Examples of image processing and analysis code for AO applications include image registration, montaging or mosaic generation, capillary tortuosity and flow, and photoreceptor, RPE, and ganglion cell identification and quantification (cone packing, tessellation, Voronoi analysis). Because only de-identified information will be processed, a direct breach of confidentiality is not possible. Moreover, because high resolution AO images of only a small patch of the retina will be acquired in one video, it is not possible to reconstruct patient identifiable vascular patterns.

De-identified images from the study will be made public in the form of presentations, peer-reviewed publications, and other scientific and educational interactions with internal and external professional colleagues, students, and other trainees. Confidentiality will be maintained through-out the reporting process.

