**Abstract**

**Objective:** The objective of the study is to collect and assess adaptive optics (AO) retinal images from human subjects in support of projects to demonstrate, advance, and enhance clinical use of AO technology.

**Study Population:** One hundred (100) healthy volunteers without eye disease and fifty (50) subjects with primary open angle glaucoma (POAG) will be enrolled.

**Design:** This is an interventional study protocol where participants will be imaged with investigational multimodal AO retinal imaging systems that include optical coherence tomography (OCT) and scanning laser ophthalmoscopy (SLO) channels. High resolution OCT and SLO videos will be collected while the instruments automatically detect and correct for image distortion caused by ocular aberrations. In general, videos of different retinal structures will be acquired from several retinal locations using various imaging modes.

**Outcome Measures:** The primary outcomes for this protocol are qualitative and quantitative assessment of the AO images and investigation of the cellular morphological and physiological changes due to glaucoma.

---

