### *3.5 Consent Process*

The PI ([name]) or co-I ([name]) will consent all FDA participants (cohort 1) prior to any activity (including the UMEA eye exam) using a standard script (Appendix 5a). The PI ([name]) or UMEA Co-I ([name]) will consent all non-FDA healthy volunteers (cohort 1) and POAG participants (cohort 2) using a similar script (Appendix 5b). [name] will recruit subjects during initial or follow-up eye exams after reviewing their medical record, POAG disease history and severity, and determining during the exam if they meet the inclusion/exclusion criteria listed above. In particular, he will judge their eligibility based upon the clarity of their anterior optics (e.g., no cataracts), their fixation ability, and their ability to keep their head motion minimal while sitting in a chin rest.

Potential participants (both cohorts) will receive a verbal explanation of the purposes, procedures, and potential risks of the study. Potential participants will have the opportunity to carefully review the informed consent form (ICF) and ask questions regarding this study prior to signing, and they will be informed that they may withdraw from the study at any time without prejudice to themselves. Potential participants will also be allowed to take the ICF home overnight to carefully consider the risks prior to consent. All participants must sign an IRB-approved ICF. A signed copy of the ICF will be provided to the participant to take home.

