## **7.0 Participant Monitoring and Adverse Event Reporting**

### *7.1 Participant Monitoring*

Participants will be monitored for adverse events by the study investigators during all imaging sessions.

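### Images are coded for confidentiality only and readers are not masked to cohort, so judged measures in the healthy-versus-glaucoma comparison are open to observer bias

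*Protocol*

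**What the plan says.** **Outcome.** The Abstract states: "The primary outcomes for this protocol are qualitative and quantitative assessment of the AO images". To this it adds a second part, the study of how glaucoma alters the structure and function of retinal cells. The first part is a judgement about images; the second is a contrast between cohorts. On the cohorts it says: "One hundred (100) healthy volunteers without eye disease and fifty (50) subjects with primary open angle glaucoma (POAG) will be enrolled".

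**Who meets the participants.** Under section 3.5 the PI or a co-investigator "will consent all FDA participants (cohort 1) prior to any activity (including the UMEA eye exam) using a standard script (Appendix 5a"), and the PI or the clinic co-investigator "will consent all non-FDA healthy volunteers (cohort 1) and POAG participants (cohort 2) using a similar script (Appendix 5b"). Section 4.3 has the PI or a co-investigator give the dilating drops. Section 5.2 allows only the subject and investigators in the imaging laboratory, and section 7.1 says: "Participants will be monitored for adverse events by the study investigators during all imaging sessions".

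**Coding.** Section 5.3 files session data under a subject number and describes a single list that ties the number to name and age. Of that list it says: "Only the study investigators will have access to this electronic document". Section 5.1 describes de-identified clinical images as carrying the subject number and no personal information.

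**Analysis.** Section 5.4 says that the videos "will be analysed with custom software written by the investigators in LabVIEW and MATLAB" or with general tools, naming ImageJ and Photoshop. Its examples include registration, montaging and cell identification. The benefit it claims for de-identification is that confidentiality cannot be directly breached.

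**The concern.** Coding for privacy and masking for measurement are different safeguards. The first stops an outsider from learning who a participant is. The second stops a reader from knowing which group an image belongs to. The protocol specifies the first in detail and makes no provision for the second.

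A reader who knows the cohort and expects damage in glaucoma may grade quality differently, accept or reject frames differently, or correct cell marks differently in the two groups. None of this need be deliberate. The resulting shift adds directly to the cohort difference. Recruiting more participants does not reduce it; a larger sample only makes a false difference look more certain.

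**Working it through.** The protocol gives no alpha, power, effect size or sample-size derivation, so there is no figure to reproduce. The check has two parts: what the text establishes, and an illustration of size.

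**Part 1: what the text establishes**

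- *Is cohort known to the investigators when images are acquired?* Yes. They consent the participants (3.5) and are present at every session (5.2, 7.1). Perimetry is done in cohort 2 only, and 4.2 lists it among the tests that guide where to image. Photoreceptor stimulation is done in healthy controls only (4.3).
- *Could cohort be inferred from the data without the name list?* Plausibly. Clinical data reach the FDA investigators under the subject number (5.1). If the perimetry record is among them, it marks that number as cohort 2.
- *Does the coding remove cohort?* No section says so. The only stated purpose is confidentiality (5.3, 5.4).
- *Are any measures judged?* The qualitative assessment is, by definition. For the quantitative measures, 5.4 lists code-based work but also permits general image-editing tools, so hand steps are possible but not documented.
- *Who reads the images?* Not stated. Section 5.4 says who writes the software and is passive about who does the analysis.

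**Part 2: illustration of size**

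From the Abstract: n1 = 100, n2 = 50. Assumed, not in the protocol: two-sided alpha 0.05 (critical value 1.96), one continuous measure per subject, independent subjects, all participants analysed, no true difference, and a reader shift of b SD in one cohort.

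SE in SD units = sqrt(1/n1 + 1/n2) = sqrt(0.01 + 0.02) = 0.1732.

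False-positive rate = Φ(b/SE − 1.96) + Φ(−b/SE − 1.96).

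For b = 0.2: b/SE = 1.155, so Φ(−0.805) + Φ(−3.115) = 0.2103 + 0.0009, about 21.1%.

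Blood-flow imaging covers only a subset whose size is not given, so the same formula is shown for an assumed 20 versus 20, where SE = sqrt(0.05 + 0.05) = 0.3162.

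| Reader shift b (SD) | 100 vs 50 | 20 vs 20 (assumed) |
|---|---|---|
| 0 | 5.0% | 5.0% |
| 0.1 | 8.9% | 6.2% |
| 0.2 | 21.1% | 9.7% |
| 0.3 | 41.0% | 15.8% |

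For the same shift, the larger sample has the higher false-positive rate, because the bias stays fixed while the standard error falls.

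**The case against.** **This may belong in a document not shown.** Who reads images, and whether they are masked, is often settled in an analysis plan or reading manual, and 5.4 says nothing false about it. This is a fair limit: absence of masking from the study as a whole is not proven. But the protocol itself fixes the coding scheme, key access and data flow, and fixes them for privacy alone. Masking has to be in place before the first image is graded. A later statistical plan cannot restore it for images already read.

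**Stronger readings are tempting and are not supported.**

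- A reader might infer that the investigators who image the participants also analyse the images. That is likely, but 5.4 says only that they wrote the software.
- A reader might infer that the identity list reveals cohort. It is described as linking number to name and age; cohort is not mentioned. The investigators' knowledge of cohort comes from consent and imaging.
- A reader might call the primary measures manual. The protocol does not. Fully automated measures carry less risk, mainly through tuning and image selection.
- A reader might take 9% to 41% as an estimate of this study's error rate. It is arithmetic on an assumed shift; the protocol gives no evidence on how large a shift would be.

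**Much of the study is not a cohort contrast.** Sections 2.0 and 4.0 stress image collection, image-quality methods and new imaging modes. Test-to-test variability work (4.3) need not compare cohorts, and the stimulation experiment (4.3) is in healthy controls only. This stands, and confines the point to the healthy-versus-POAG comparison, which the Abstract nevertheless places among the primary outcomes.

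**Recoding could break needed links.** Montaging needs files from one eye kept together, room-air and oxygen images must be paired, repeat sessions must be matched, and cell dimensions need each subject's biometry. This also stands, so the code must be set per subject and eye and not per file.

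**Conclusion.** The concern holds for the judged parts of the cohort comparison: the qualitative primary assessment and any frame selection, hand marking or correction. As written, the protocol leaves these open to observer bias because cohort is known to the investigators at consent and imaging, they hold the key, and the coding serves confidentiality only.

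The size of the bias is unknown. The illustrative rates (about 9% to 41% with 100 versus 50; about 6% to 16% with an assumed 20 versus 20) rest on an assumed reader shift of 0.1 to 0.3 SD, an assumed two-sided 5% test, one independent measure per subject and no true difference. The conclusion does not depend on them. It would fall away if a reading manual or analysis plan already provides masked reading.

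This should be corrected. It does not call into question the image-quality and method-development work that involves no comparison between cohorts.

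**What to change.** Add a paragraph to section 5.4 for all healthy-versus-POAG comparisons:

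- Before reading, replace the subject number with a random reading code per subject and eye. The code keeps linked files, air and oxygen pairs, repeat sessions and biometric scaling together, and removes cohort, perimetry and procedure labels.
- Name who reads the images. Qualitative grading, frame selection and any hand marking or correction are done with both cohorts in mixed order, by a reader who does not hold the key.
- An existing study member who does not read the images holds the key. The role of the person who de-identifies the clinical data cannot be confirmed from the text shown, so the rule should state the condition and not assume that this person meets it.
- Fix software settings identically for both cohorts, and freeze the measurements before cohort is merged.

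The cost is some data-handling work, since section 5.1 notes that datasets can reach tens of gigabytes per subject and session. No extra visits, participants or readers are needed. Masking will be imperfect where glaucoma damage is visible in the image or the reader remembers the session. It also cannot undo the choice of imaging sites made from the clinical tests, which section 4.2 makes deliberately.

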#### *5.5 Study Conclusion*

At the conclusion of the study, all data will be removed from shared drives and archived on external hard drives. Documents containing any PII or documents that link the subject's identification to the de-identified data will be destroyed 5 years after study termination.

### **6.0 Patient Risks**

#### *6.1 Summary of Potential Risks*

In general, there are four potential risks to the participants in this imaging study:

1. The participant has an allergic reaction or other complication to the mydriatic agent (increase in intraocular pressure),
2. The participant is exposed to a light level that exceeds the maximum permissible exposure (MPE) limit that damages the retina,
3. The participant becomes injured during imaging from their presence in a research laboratory setting near scientific instrumentation, and
4. The participants experience side effects from continuous oxygen supplementation.

Mydriatic drugs work by inhibition of the parasympathetic (i.e., contractive) response of the eye by blockage of muscarinic acetylcholine receptors or by stimulus of the sympathetic response of the eye by blockage of the re-uptake of noradrenaline. Side effects and complications associated with mydriatic drugs include photophobia, and in extremely rare cases, an increase in intraocular pressure leading to acute glaucoma. Mydriatic drugs are necessary for this investigation because the benefit from adaptive optics is optimal for dilated pupils larger than 6 mm. Only those subjects known (from clinical administration conducted by [name]) not to have severe adverse reactions to mydriatic agents will be enrolled in the study. All participants will experience some level of photophobia similar to that associated with a routine visit to their ophthalmologist. The effect of the drugs usually lasts 4-6 hours.

The second risk, light exposure to focused (ANSI) Class II or higher laser power levels, has to do with the interaction between imaging beams that are directed to the participant eyes and their retina (the only reason the device is minimally invasive rather than non-invasive). The light safety analyses in Appendix 2a, 2b, and 2c describes the technical details of the risk. Given the mitigation strategy, this risk has a very low likelihood of occurring but moderate severity if it does occur.

The third risk involves injuries that can occur when a participant unfamiliar with research enters a laboratory. The optics laboratory is not a wet lab, and so does not have harmful chemicals. The patient has one ingress/egress path to the AO imaging systems. Therefore, this risk has a very low likelihood of occurring and low severity if it does occur. This protocol and the imaging procedures described, as well as the eye exam, have been examined by the CDRH safety officer and found to be acceptable (Appendix 6).

A fourth risk for the subset of subjects that undergo oxygen supplementation includes restriction of facemask air-flow leading to hypoxia, and possible side effects from continuous oxygen inhalation (dry nose, bloody nose, fatigue, or headaches). The side effects are dependent on the duration and intensity of the oxygen delivery. Oxygen supplementation will be set to a rate of 10-15 L/min for delivery via the non-rebreather face mask. Oxygen saturation levels will be closely monitored using standard pulse oximetry. Therefore, this risk has a very low likelihood of occurring. If the subjects exhibit any side effects, we will terminate the experiment immediately. If an adverse event occurs, the subject will be monitored on-site for an hour until symptoms resolve. If any issues persist, [name] will be contacted (if not already present) and the subject will be taken to UMEA. For an adverse event that is deemed by the investigators to be serious or potentially serious, 911 will be called. As per normal laboratory safety practice, oxygen cylinders will be kept away from heat sources and electrical hazards to ensure the safety of the laboratory setting.

### *6.2 Risk Mitigation Strategy*

We will recommend that each subject avoids sunlight and wears sunglasses outside to mitigate photophobia. More severe complications (allergic reaction to mydriatic drugs) will be monitored by the Medical Advisor for 30 minutes after administration during the initial UMEA eye exam and by the PI and co-Is during the imaging sessions. The eye exam is designed to provide significant reduction in risk of reaction by screening subjects with a predisposition or history of AACG.

The primary mitigation for the second risk is to maintain power levels that are below ANSI MPE limits. The power at the cornea will be measured each day an imaging session takes place and recorded in a logbook. The SLO and OCT illumination sources are superluminescent diodes (SLD), the output power of which are controlled from the computer. The SLD electronic drive boards have current limits that prevent excessive output power being delivered to the participant's eye. When SLDs fail, their power output will drop significantly or altogether (i.e., the power never increases for device failure). Scanner failure will direct a focused beam to the retina but also stop imaging, which will be nearly immediately noticed by the operator (within seconds), who can tell the subject to sit back from the instrument. The visible light stimulus source delivery is controlled with a shutter that precisely sets the illumination timing (pulse duration, etc.). The SLO line-scanning mode (for RBF imaging) will be configured to interleave line and raster frames so that the line scan is only stationary for 37 ms.

The third and fourth risks are mitigated by common laboratory safety practices that are in place at DBP and described in our BSC safety manual, which contains the emergency response plan as well as a description of procedures for dealing with chemical safety, biosafety, laser safety, and issues related to hazardous waste. OSEL complies with all Occupational Safety and Health Administration (OSHA) regulations and conducts routine safety training for its staff. Additionally, the fourth risk will be mitigated by having a dedicated technician monitor airflow, pulse oximetry measurements, blood pressure, ECG, and patient status for signs of fatigue or discomfort continuously during imaging. The participant will be queried through-out to check for side effects of oxygen supplementation.

